8 STATISTICAL DESIGN AND ANALYSIS

The primary efficacy endpoint is based on comparison to pre-specified performance goal based of the EXCEL study³. The study is powered at 80% to show non-inferiority of the BiOSS LIM C compared with XIENCE EES. The primary analysis will be based on an intent-to-treat (ITT) patient population.

The ITT population set consists of all patients who have provided informed consent and have been enrolled. All patients will be analyzed according to assigned treatment group, regardless of the treatment actually received.

8.1 Primary Analysis

The primary analysis is an analysis of the primary endpoint, being PoCE at 12-months. The study is powered at 80% to show non-inferiority for the BiOSS LIM C when compared to XIENCE. The BiOSS LIM C suspected PoCE assumption is based on the assumption of no difference in event rates between BiOSS LIM C and XIENCE.

The 95% one-sided confidence interval will be calculated for the PoCE rate at 12 months, using Kaplan-Meier estimates at 12 months and its standard deviation; the KM-estimate is assumed to be normally distributed.

The upper limit of the interval will be compared with a performance target, being the reported PoCE in the EXCEL trial plus a non-inferiority margin. If the 95% interval excludes the performance target, BiOSS LIM C will be considered to be non-inferior to XIENCE (this accounts to an one-sided non-inferiority testing with a significance level (alpha of 5%).

Statistical analyses will be performed with either SAS software system (SAS Institute Inc., Cary, North Carolina) version 9.3 or higher.

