8.2 Sample Size Calculations

Assumptions:

Power = 80%

One-sided alpha = 5%

Non-inferiority margin of 6.3%

XIENCE PoCE – 16.7% at 12M (Reference: EXCEL study, PCI cohort, data on file).

Confidential and Proprietary

Do not distribute or reproduce without the prior written permission of ECRI.

Protocol Version 1.2 – 02 Oct 2018

The BiOSS LIM C expected PoCE assumption is based on an assumed no difference in event rate as compared to the objective performance goal (OPC – EXCEL study).

A sample size calculation of 256 analyzable patients is required using the assumptions above, PASS software, and a non-inferiority Fisher Exact test for one proportion. This number is increased to 260 patients accounting for some attrition.

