8.6 Missing data

Every effort will be undertaken to minimize missing data. Kaplan-Meier estimates will censor incomplete data at the date of last available follow-up information, assuming complete reporting of all events up to that date and event status unknown after that date.

Other missing information will be assumed Missing Completely at Random (MCAR). No imputation will take place for these data, nor is any sensitivity analysis planned.

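### The untransformed Kaplan-Meier limit in the primary test has a real one-sided error of about 6%, not the stated 5%; only a borderline result is affected

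*Combined protocol and SAP*

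**What the plan says.** Section 8.1 (Primary Analysis) states: "The 95% one-sided confidence interval will be calculated for the PoCE rate at 12 months", obtained "using Kaplan-Meier estimates at 12 months and its standard deviation; the KM-estimate is assumed to be normally distributed". The normality is placed on the estimate itself, and no log, log-log or other transformation is named.

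The decision rule follows: "The upper limit of the interval will be compared with a performance target", which is described as the EXCEL PoCE rate plus a non-inferiority margin. "If the 95% interval excludes the performance target, BiOSS LIM C will be considered to be non-inferior to XIENCE". The section adds that this corresponds to a one-sided test at 5%.

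Section 8.2 (Sample Size Calculations) gives the reference rate of 16.7%, the margin of 6.3%, one-sided alpha of 5% and power of 80%. It then says: "A sample size calculation of 256 analyzable patients is required using the assumptions above", using "PASS software, and a non-inferiority Fisher Exact test for one proportion". Enrolment is raised to 260 to allow for attrition. Section 8.6 (Missing data) says: "Kaplan-Meier estimates will censor incomplete data at the date of last available follow-up information".

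**The concern.** An untransformed normal limit for a proportion takes its standard error at the observed rate. To pass, the observed rate must lie well below 23.0%, and there the standard error is smaller than at 23.0%. The limit is therefore a little too low, and the device passes somewhat too often when its true rate is at the target. The direction is systematic and favours the device.

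This is the trial's only confirmatory comparison, it has no concurrent control, and no alternative analysis of the primary endpoint is specified that would show a result to depend on the choice of limit. In addition, the test that sizes the trial in 8.2 is not the test that decides it in 8.1. The 5% and 80% therefore describe neither the error nor the power of the planned rule.

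**Working it through.** **Inputs.** Reference rate 16.7%, margin 6.3 points, alpha 5% one-sided, power 80%, 256 analyzable and 260 enrolled patients (8.2); one-sided 95% Kaplan-Meier limit, normal on the raw scale (8.1). Target: 16.7% + 6.3% = 23.0%. This is derived; the plan does not print it.

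**The plan's own figure.** The one-sample normal formula with null variance gives

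n = [1.64485 × √(0.23 × 0.77) + 0.84162 × √(0.167 × 0.833)]² / 0.063² = 255.04, rounded up to 256.

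So 256 reproduces, but from a normal approximation. An exact binomial test at n = 256 has 78.9% power.

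**Error of the planned rule.** With complete follow-up the Kaplan-Meier estimate is x/n and its Greenwood standard error is √[p̂(1 − p̂)/n]. For each n, find the largest x with p̂ + 1.645 × SE < 0.23. The error is then the exact binomial P(X ≤ x) at 0.23, and the power is the same probability at 0.167.

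- n = 256, x = 48: 0.1875 + 1.645 × 0.02439 = 0.2276, passes. x = 49: 0.1914 + 1.645 × 0.02459 = 0.2319, fails.
- n = 260, x = 49: 0.1885 + 1.645 × 0.02425 = 0.2284, passes. x = 50: 0.1923 + 1.645 × 0.02444 = 0.2325, fails.

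For comparison, the standard error at the target with n = 260 is √(0.23 × 0.77/260) = 0.0261, against 0.0243 at 49 events.

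| Limit | n | Passes with up to | Error at 23.0% | Power at 16.7% |
|---|---|---|---|---|
| Untransformed (planned) | 256 | 48 | 5.91% | 83.3% |
| Untransformed (planned) | 260 | 49 | 6.21% | 84.4% |
| Log-log | 256 | 47 | 4.29% | 78.9% |
| Log-log | 260 | 48 | 4.53% | 80.2% |
| Exact binomial | 256 | 47 | 4.29% | 78.9% |
| Exact binomial | 260 | 48 | 4.53% | 80.2% |

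Error over n = 250–260:

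- Untransformed: 5.18% (n = 258) to 6.72% (n = 254), mean 6.0%. It is above 5% at every n.
- Log-log: 4.00% (n = 257) to 5.26% (n = 253), mean 4.6%.
- Exact binomial: 3.7–4.9%.

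**Where the verdict changes.** With 49 events in 260 (18.8%) the planned limit is 22.8% and passes. On the log-log scale S = 0.8115 and log(−log S) = −1.5663, with standard error 0.02425/(0.8115 × 0.2088) = 0.1431. The upper limit is 1 − exp{−exp(−1.5663 + 1.645 × 0.1431)} = 23.2%, which fails. The exact limit, 23.3%, also fails. The probability of exactly 49 events is 1.7% at a true rate of 23.0% and 4.2% at 16.7%.

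**Censoring.** Kaplan-Meier/Greenwood simulations rest on assumptions that are not in the documents:

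- n = 260, losses of 0–5% at uniform times, events uniform over the year or 30% in the first week, 20,000 trials per setting: error 5.8–6.3% untransformed and 4.3–4.8% log-log; power 82.9–84.5% and 78.6–80.5%.
- n = 256 and 260, losses of 0–10%, 40% of events early, 40,000 trials per setting: error 5.9–6.3% untransformed.

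**The case against.** The strongest reply is that this is ordinary approximation error. The method is pre-specified, the normality assumption is stated openly, and the excess is about one point. This stands as a statement of size: a clear result either way is unaffected.

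The error range over 250–260 can also be challenged. The analysis keeps all enrolled patients and censors incomplete ones, so the planned n is 260, and 256 is the only other figure given. That is fair: 6.2% and 5.9% are the figures to cite, and the range only shows how the error moves with n. Both exceed 5%.

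The log-log limit is approximate too. At n = 253 and n = 258 it accepts the same count as the planned rule, with error 5.26% and 5.18%. It also costs power: at n = 260 the error falls by 1.7 points (6.21% to 4.53%) and power by 4.2 points (84.4% to 80.2%). Both facts stand and belong in the plan.

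The mismatch between 8.1 and 8.2 is harmless for power, since the planned rule has more than 80%. But part of that power comes from running above 5%.

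Finally, the 12-month visit window of ±30 days could add late censoring. With half of the patients censored uniformly over days 335–365 and 1.5% lost (assumed), the error was about 6.5% untransformed and 4.8% log-log. This widens the range for the planned rule and leaves the direction unchanged.

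**Conclusion.** The concern holds. As written, the primary rule is not a 5% test: its one-sided error is 5.9% at 256 patients and 6.2% at 260. These figures assume a true rate of exactly 23.0%, complete follow-up and the plain reading of 8.1 as an untransformed limit. Non-informative losses of 0–10% leave the error at about 6%. The excess favours the device and moves the pass threshold by at most one event over n = 250–260. It should be corrected because it lies in the only confirmatory test, and a change of method after a borderline result would not be credible. It does not threaten the trial as a whole.

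**What to change.** In 8.1, replace the normal-theory limit by the one-sided 95% upper limit of the Kaplan-Meier event rate on the complementary log-log scale (SAS PROC LIFETEST, CONFTYPE=LOGLOG), and print the 23.0% target. Name the transformation explicitly: a limit on the plain log-survival scale does worse, with error 5.6–7.5% over n = 250–260.

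In 8.2, name the same test as in 8.1. State its alpha as approximately 5% (4.0–5.3% over n = 250–260) and its power as about 79–80%. An exact binomial limit would guarantee 5% but cannot handle the censoring foreseen in 8.6.

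The cost is one sentence and one software option in 8.1, one sentence in 8.2, and no extra patients. Power drops from 83–84% to 78.9% at 256 and 80.2% at 260 (78.1–81.8% over n = 256–260), so it may fall slightly short of the stated 80%. The log-log limit lowers the error on average but does not guarantee 5% at every n.

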Statistical Analysis Plan	
Primary Analysis: The primary efficacy endpoint is based on comparison to pre-specified performance goal based on the PCI arm of the EXCEL study³. The study is powered at 80% to show non-inferiority of the BiOSS LIM C compared with XIENCE EES. The primary analysis will be based on an intent-to-treat (ITT) patient population.
 
Assumptions: Power = 80% One-sided alpha = 5% Non-inferiority margin of 6.3% PCI (XIENCE) PoCE – 16.7% at 12 months (365 days)³ (EXCEL study, PCI cohort, data on file). The BiOSS LIM C expected PoCE assumption is based on an assumed no difference in event rate as compared to the objective performance goal (OPC – EXCEL study).
 
Study Sample Size Calculation: 260 Patients A sample size calculation of 256 analyzable patients is required using the assumptions above, PASS software, and a non-inferiority Fisher Exact test for one proportion. This number is increased to 260 patients accounting for some attrition.

1.1 Schedule of Assessments:

Schedule of Events	Baseline (prePCI)	Procedure	Post- procedure/ Discharge	30 days (±7 days)	6 months (±14 days)	1 year (±30 days)
				Visit	TC Contact	Visit
Inclusion/Exclusion Criteria	•					
Pregnancy test*	•					
Left Main Medina class**	•					
SYNTAX Score	•		• ⁹			
Informed Consent	•					
Demographics, Medical History, vital signs	•					
Anginal status	•		•	•	•	•
12-Lead ECG	• ¹		• ²	•		•
LVEF	• ³					
Blood Laboratory (WBC, platelets, Hemoglobin, Hematocrit, serum Creatinine, HbA1c)	• ⁴					
Cardiac enzymes (CKMB, Troponin)	• ⁵		• ⁶			
Cardiac Medications	•		•	•	•	•
Angiography ⁷	•	•				
iFR ⁷		• ⁱ				
IVUS ⁷		• ⁱⁱ				
Serious Adverse Events ⁸		•	•	•	•	•

Notes:

*For females of childbearing-potential only

**Diameter Stenosis (DS%) and Medina class of the distal left main must be confirmed by the academic core lab in Rotterdam using dedicated QCA bifurcation software prior to enrollment.

¹ ECG at time of screening must be performed within 72 hours prior to PCI procedure.

² ECG within 24 hours post-procedure or at discharge, whichever comes first.

³ Left ventricular ejection fraction (LVEF) must be assessed within 14 days prior to enrollment, either by echocardiography, MRI, or contrast left ventriculography.

⁴ Blood chemistry: WBC, Platelets, Hb, Ht, serum Creatinine, HbA1c) at time of screening must be performed within 28 days prior to PCI procedure

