3 OBJECTIVE

To establish the safety and efficacy of the BiOSS LIM C with respect to Patient oriented Composite Endpoint (PoCE) at 12 months in a “real world” left-main bifurcation population and compared with a pre-specified performance goal.

**Since the sample size and power calculation of the POLBOS LM study is based on the outcome of the EXCEL trial as an objective performance goal, the in- and exclusion criteria, general recommendations for practice, treatment and (endpoint) definitions are similar to the EXCEL protocol as published in NEJM and referred as such.³*

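### Section 8.1 tests one arm against a fixed 23.0% goal but concludes non-inferiority to XIENCE at alpha 5%, an error rate that the planned rule does not deliver for that claim

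*Combined protocol and SAP*

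**What the plan says.** The objective in section 3 is to establish 12-month PoCE in a "left-main bifurcation population and compared with a pre-specified performance goal". The synopsis describes a "performance goal based on the PCI arm of the EXCEL study".

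Section 8.1 builds a one-sided 95% limit from the Kaplan-Meier estimate and its standard deviation, where "the KM-estimate is assumed to be normally distributed". The upper limit is set against a target, "being the reported PoCE in the EXCEL trial plus a non-inferiority margin". Section 8.2 gives the two parts: 16.7% ("Reference: EXCEL study, PCI cohort, data on file") and 6.3%. Their sum, 23.0%, is not printed.

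The conclusion drawn is comparative: "If the 95% interval excludes the performance target, BiOSS LIM C will be considered to be non-inferior to XIENCE". Section 8.1 describes the rule as "an one-sided non-inferiority testing with a significance level (alpha of 5" per cent. Section 8 attaches the power to the same comparison: "The study is powered at 80% to show non-inferiority of the BiOSS LIM C compared with XIENCE EES". The synopsis and section 8.1 also tie the 80% to XIENCE.

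**The concern.** The only variance in the test is that of the single arm. The EXCEL rate enters as a known constant, although it is an estimate from a finite cohort. A test of this kind answers whether the BiOSS LIM C rate is below 23.0%. It does not answer, at the same error rate, whether BiOSS LIM C is within 6.3 points of XIENCE.

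The protocol draws this distinction itself. Section 2.1 names two possible trials: a randomised non-inferiority trial against a conventional stent, or an assessment against a performance index. The second was chosen, but section 8.1 states the conclusion that belongs to the first. A positive result would be reported as a 5%-level comparative finding when its error rate is higher and the comparison is not randomised.

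**Working it through.** **Inputs.** From section 8.2: one-sided alpha 5%, power 80%, benchmark 16.7%, margin 6.3 points, expected rate 16.7%, 256 analysable and 260 enrolled. From section 2.1: EXCEL had 1905 patients in total. Assumed: a PCI cohort of 950 (about half of 1905). 760 is 80% of 950, using the rounded share of bifurcation cases in section 2.1. 500 and 1905 are shown as outer values. Censoring is ignored throughout.

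**1. The plan's own sample size.** With p0 = 0.23 and p1 = 0.167,

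n = [(1.645·√(0.23·0.77) + 0.842·√(0.167·0.833)) / 0.063]² = [(0.692 + 0.314) / 0.063]² = 255.04, so 256. The stated figure reproduces.

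**2. The planned limit against a fixed 23.0%.** The rule passes if p̂ + 1.645·√(p̂(1−p̂)/n) < 0.23. At n=260, 49 events give p̂ = 18.85% and a limit of 22.84%, and 49 is the highest passing count. The exact binomial probability of 49 or fewer at a true rate of 23% is 6.2%. Power at 16.7% is 84.4%.

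| n | highest passing count | false-positive rate |
|---|---|---|
| 256 | 48 | 5.9% |
| 257 | 48 | 5.5% |
| 258 | 48 | 5.2% |
| 259 | 49 | 6.6% |
| 260 | 49 | 6.2% |

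This part comes from the normal approximation and discreteness. EXCEL plays no role in it.

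**3. The claim about XIENCE.** Take the true XIENCE rate as 16.7% and the true BiOSS LIM C rate as 16.7 + 6.3 = 23.0%. Let the EXCEL count x follow Bin(N, 0.167), so that the target is x/N + 0.063. The false-positive rate is

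Σ Pr(x) · Pr[Bin(260, 0.23) ≤ c(x)],

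where c(x) is the highest count that passes against that target.

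| Assumed EXCEL PCI cohort N | planned limit | exact one-proportion test |
|---|---|---|
| 500 | 9.3% | 7.2% |
| 760 | 8.3% | 6.2% |
| 950 | 7.8% | 5.8% |
| 1905 (all of EXCEL) | 6.9% | 5.1% |
| fixed goal, no EXCEL error | 6.2% | 4.5% |

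At 950, EXCEL's error adds 7.8 − 6.2 = 1.6 points under the planned limit. The total is 7.7-8.0% over n=256-260. As a large-sample check without discreteness, the standard errors are √(0.23·0.77/260) = 2.61 points and √(0.167·0.833/950) = 1.21 points. Then Φ(−1.645·2.61/√(2.61² + 1.21²)) = 6.8% in place of 5.0%.

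**4. The exact test of section 8.2 against the fixed goal.** At n=260 it passes at 48 or fewer events: alpha 4.5%, power 80.2%. At n=256 it passes at 47 or fewer: alpha 4.3%, power 78.9%.

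**5. Where the two conclusions part.** Take EXCEL at 16.7% of 950. With 49/260 events the one-sample limit is 22.8%, so the goal is met. The upper limit for POLBOS minus EXCEL, 18.85 − 16.7 + 1.645·√(2.43² + 1.21²), is 6.6 points, above 6.3. With 48 events both pass (22.4%; 6.2 points).

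**The case against.** The strongest reply is that a fixed, pre-specified goal is the usual frame for a single-arm device study, and error conditional on that goal is the usual error rate. The objective is worded that way, section 8.1 spells out the rule openly, and averaging over a completed trial is a different frame. This stands as a defence of the design, and the goal should be kept. It does not defend a conclusion about XIENCE, which is what section 8.1 draws.

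The case against the size of the effect also has force:

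- Most of the EXCEL-related figures rest on a cohort size that the documents do not give.
- A reader might infer that ignoring EXCEL's error by itself turns 5% into 7.8%. It does not: 1.2 of the 2.8 excess points at n=260 are already present against the fixed goal.
- The 49-event example is a knife-edge. It is the only count at which the two limits disagree at 950, and the exact test also fails there.

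Sections 3 and 8.5 align criteria, definitions and day 0 with EXCEL. That bears on comparability and leaves the sampling error of the 16.7% where it was.

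**Conclusion.** The mismatch between test and conclusion is certain from the text. Its numerical size is modest. For the claim about XIENCE, the planned rule has a false-positive rate of about 7.8% at an assumed 950 PCI patients, 9.3% at 500, and 6.9% even on the impossible reading that all 1905 EXCEL patients had PCI. So 5% is not met at any cohort size tried. These figures assume a true XIENCE rate of 16.7%, comparable populations and no censoring.

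Two further readings are not supported. One is that the trial is underpowered or mis-sized: 256 reproduces, and averaged over EXCEL's error the planned limit still has about 80% power (81.3% at 950, 79.8% at 500). The other is that rewording the conclusion makes the 5% label true: against the fixed 23.0% the normal-theory limit has 5.2-6.6%, so the label needs its own correction.

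**What to change.** 1. In section 8.1, word primary success as having met the pre-specified performance goal of 23.0%, print that number, and remove the statement of non-inferiority to XIENCE.
2. In the synopsis, the opening of section 8 and section 8.1, attach alpha and power to the goal only.
3. Make the alpha label true in one of two ways. Either base the decision on the exact one-proportion test already named in section 8.2 (48 or fewer of 260, or 47 or fewer of 256), or keep the Kaplan-Meier normal limit and state its actual error of about 5-7%.
4. Optionally, report a one-sided 95% limit for POLBOS minus EXCEL that includes EXCEL's variance, labelled as supportive, unadjusted and non-confirmatory. At an assumed 950 it has alpha about 5.7% and power about 77%. It needs EXCEL's patient and event counts.

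The goal and the sample size stay as they are. The costs are that the comparative headline is given up, that the exact rule allows one event fewer, and that the exact rule needs a stated way of counting patients without complete 12-month status, whom section 8.6 now handles by censoring. With 256 analysable patients its power is 78.9%, just under the stated 80%.

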8.2 Sample Size Calculations

Assumptions:

Power = 80%

One-sided alpha = 5%

Non-inferiority margin of 6.3%

XIENCE PoCE – 16.7% at 12M (Reference: EXCEL study, PCI cohort, data on file).

Confidential and Proprietary

Do not distribute or reproduce without the prior written permission of ECRI.

Protocol Version 1.2 – 02 Oct 2018

The BiOSS LIM C expected PoCE assumption is based on an assumed no difference in event rate as compared to the objective performance goal (OPC – EXCEL study).

A sample size calculation of 256 analyzable patients is required using the assumptions above, PASS software, and a non-inferiority Fisher Exact test for one proportion. This number is increased to 260 patients accounting for some attrition.

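### The 80% power and 5% one-sided alpha stated for the trial are not those of the Kaplan-Meier rule in section 8.1 that decides it; 256 itself is not an error

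*Combined protocol and SAP*

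**What the plan says.** Section 8.2 lists the design inputs: 80% power, "One-sided alpha = 5" percent, "Non-inferiority margin of 6.3" percent, and a reference rate given as "XIENCE PoCE – 16.7% at 12M". The rate expected with the study stent equals the reference: "The BiOSS LIM C expected PoCE assumption is based on an assumed no difference in event rate as compared to the objective performance goal". From these it derives 256 analyzable patients, using "PASS software, and a non-inferiority Fisher Exact test for one proportion". It then adds four: "This number is increased to 260 patients accounting for some attrition". The statistical entry in the synopsis repeats the same calculation.

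Section 8.1 sets the deciding analysis. The one-sided 95% interval for the 12-month PoCE rate is obtained "using Kaplan-Meier estimates at 12 months and its standard deviation; the KM-estimate is assumed to be normally distributed". Its upper limit is compared with the EXCEL rate plus the margin, and the section equates this with a one-sided test at 5%. The same section says "The study is powered at 80% to show non-inferiority for the BiOSS LIM C when compared to XIENCE".

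Neither section links the exact test to the Kaplan-Meier limit, or calls one an approximation to the other.

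**The concern.** Three methods are in play: the exact test that section 8.2 names, the formula that produces 256, and the Kaplan-Meier limit that section 8.1 will apply. In a single-arm trial with one pass-or-fail comparison against a fixed target, power and type I error belong to a particular rule. If they are quoted for one rule while another decides, readers do not know the risk that a stent with a true rate of 23.0% is declared non-inferior. There is also a result on which the named test and the planned rule give opposite answers. Finally, Fisher's exact test is normally a comparison of two groups, so the label does not identify a test for one arm against a fixed target.

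**Working it through.** **Inputs** (sections 8.1 and 8.2): expected rate 0.167; target 0.167 + 0.063 = 0.230; one-sided alpha 0.05 (z = 1.645); power 0.80 (z = 0.842); n = 256 analyzable, 260 enrolled.

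**1. Reproducing 256.** The one-sample normal approximation, with the null variance for alpha and the alternative variance for power, is

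n = [(z_alpha × √(0.23 × 0.77) + z_power × √(0.167 × 0.833)) / 0.063]²

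- z_alpha × √(0.23 × 0.77) = 0.6922
- z_power × √(0.167 × 0.833) = 0.3139
- n = (1.0061 / 0.063)² = 255.04, rounded up to 256

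(z-values unrounded.) The formula's own power at 256 is 80.1%. The stated number and the stated 80% therefore reproduce, but from a normal approximation.

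**2. The exact one-sample binomial test.** Take the largest c with P(X ≤ c | n, 0.23) ≤ 0.05; power is P(X ≤ c | n, 0.167). At 256, c = 47. At 260, c = 48.

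**3. The section 8.1 rule.** With complete follow-up, the Kaplan-Meier estimate is the simple proportion p = x/n and its standard error is √(p(1 − p)/n). The rule passes when p + 1.645 × SE < 0.230.

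- 48/256: 0.1875 + 1.645 × 0.0244 = 0.2276, pass. 49/256: 0.2319, fail.
- 49/260: 0.1885 + 1.645 × 0.0243 = 0.2284, pass. 50/260: 0.2325, fail.

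Its power and alpha are the binomial probabilities of passing at 0.167 and at 0.230.

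| n | Rule | Passes at | Power | One-sided type I error |
|---|---|---|---|---|
| 256 | Exact binomial | ≤ 47 | 78.9% | 4.3% |
| 256 | Section 8.1 limit | ≤ 48 | 83.3% | 5.9% |
| 260 | Exact binomial | ≤ 48 | 80.2% | 4.5% |
| 260 | Section 8.1 limit | ≤ 49 | 84.4% | 6.2% |

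The section 8.1 rule is more liberal because its standard error uses the observed rate. Near the pass mark that rate is below 23.0%, so the standard error is smaller than the one that applies at the target.

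**4. Where the rules disagree.** With 49 events in 260, section 8.1 declares non-inferiority and the exact test does not. If the true rate is 16.7%, exactly 49 events occurs with probability about 4% (84.4% − 80.2% = 4.2 points).

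**5. Some censoring.** A simulation with the Greenwood standard error (20,000 runs; assumed timing: 40% of events in the first three days, the rest spread evenly over the year) gave, for 260 enrolled, 84.4% power and 6.4% alpha with 1.5% of patients lost, and 83.5% and 5.8% with 5% lost. Event timing and loss are assumptions; the documents give only the four extra patients.

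**The case against.** The strongest reply is that sizing on a simple binomial method and analysing by Kaplan-Meier is common and usually harmless. Here 256 reproduces from the plan's own inputs, section 8.1 does pre-specify the deciding rule, and that rule has more than 80% power. All of this stands. It is why the point is an inconsistency and not a fault in the sample size.

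A reader might still infer more, and the documents do not support it:

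- **That the trial is underpowered, because the exact test has 78.9% power at 256.** The gap of 1.1 points is the saw-tooth of a discrete test: exact power is 80.5% at 254, 81.0% at 259 and 80.2% at 260. The exact test is also not the planned analysis.
- **That the four-patient allowance fails to protect power.** Exact power does dip to 78.0% at 257 and 77.2% at 258, but this supposes that patients with incomplete follow-up are removed. Section 8 defines an intent-to-treat set of all consented and enrolled patients, section 8.6 censors incomplete follow-up at last contact, and section 7.11 keeps the data of withdrawn patients unless they forbid their use. A complete-case set of 256 to 258 is not what the plan would analyse.
- **That 273 patients are needed because exact power stays at or above 80% only from there.** This is the same saw-tooth, and no section sets such a requirement.

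What the reply does not answer is type I error. Section 8.1 states 5% for its own rule, and the rule does not hold it.

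**Conclusion.** The point holds as an inconsistency that is cheap to correct. The test named in section 8.2 is not the method that yields 256, and neither is the rule that decides the trial. For the section 8.1 rule at 260, power is about 84% instead of 80%, and one-sided type I error about 6% instead of 5%. Part of the extra power is bought by the extra type I error. The named test and the planned rule differ by one event at both 256 and 260, so they give opposite conclusions at 48 of 256 or 49 of 260.

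These figures assume complete follow-up, a true rate of 16.7% for power and 23.0% for alpha, and the target taken as fixed at 23.0%. The simulated cases with light censoring do not change the picture. The sample size need not change.

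**What to change.** In section 8.1, section 8.2 and the synopsis, name one test, remove the Fisher label, and say that 256 comes from a one-sample normal approximation. Then state the power and the actual type I error of the rule that will be used. Either of two routes is coherent:

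- **Keep the Kaplan-Meier limit.** Report about 84% power with about 6% one-sided type I error at 260, assuming complete follow-up. The power should not be quoted without the alpha.
- **Use a limit that holds 5%.** For example, an exact binomial rule passing at 48 or fewer events in 260 has alpha 4.5% and power 80.2%. A count-based rule also needs a stated way to handle censored patients.

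Both routes cost wording only and add no patients. The first requires admitting an alpha above 5%. The second gives up about four points of power (84.4% − 80.2%) and lowers the pass mark by one event. The choice should be made before outcome data are examined.
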